2.1.1.2 Definition of ACPRs

Uncorrected ACPR at Day X where X=15, 29, or 43

- A patient is considered as non-responder at Day X if the patient experiences an ETF, LCF from Day 5 to Day X, or LPF from Day 8 to Day X.
- A patient is also considered as non-responder if the parasite is not cleared by Day X unless the patient discontinues the study prior to Day X without ETF or LCF or LPF, in which case the response is considered as missing. Note that if a patient takes non-study antimalaria medications during the treatment period, the patient is considered as non-responder.

- A patient is considered as responder (Uncorrected ACPR) at Day X if the patient is not classified as a non-responder at Day X and the patient has a malaria blood film showing absence of parasite at Day X or later if Day X is missing.
- The response for a patient is considered as missing/undetermined if the patient is not classified as a non-responder prior to Day X and the malaria blood film result at Day X is missing and not followed by a subsequent negative result.

PCR-corrected ACPR at Day X where X=15, 29, or 43

- A patient is considered as non-responder at Day X if the patient experiences an ETF or LCF from Day 5 to Day 7.
- A patient is also considered as non-responder if the initial parasite is not cleared by Day X unless the patient discontinues the study prior to Day X without ETF or LCF or LPF, in which case the response is considered as missing. Note that if a patient takes non-study antimalaria medications during the treatment period, the patient is considered as non-responder.
- A patient is considered as non-responder at Day X if the patient has a parasite recrudescence from Day 8 to Day X
- A patient is considered as responder (corrected ACPR) at Day X if the patient is not classified as a non-responder by Day 7 and has negative results at Day X based on microscopy and PCR genotyping.
- A patient is considered as responder at Day X if the patient is not classified as a non-responder at Day X and the patient has a malaria blood film showing absence of parasite at Day X or later if Day X is missing.
- A patient is considered as responder at Day X if the patient is not classified as a non-responder at Day X and the patient has a malaria blood film showing new infection **at** Day X using PCR genotyping or later if Day X is missing.
- The response for a patient is considered as missing/undetermined (e.g., due to missing PCR data or miss blood smear data) if

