 - The patient, not classified as non-responder at Day X, has parasite present from Day 8 to Day X for which the PCR genotyping of recrudescence or new infection is not determined.
 - The patient is not classified as a non-responder at Day X and the malaria blood film result at Day X is missing and not followed by a subsequent negative result/new infection.
 - The patient has parasite cleared by Day 7 but has a new infection/negative PCR prior to Day X, ie, new infection/negative PCR at a visit causes PCR-corrected ACPR status unknown in later visit(s).

Note - In the context of derivation of ACPR status at Day X, the 'Day X' is referred to as the Day X analysis visit. For e.g., ACPR status at Day 29 is referred to as the ACPR status at Day

29 analysis visit. Analysis visit X will be derived using the day actual visit as defined in Tables 5-5 and 5-6. Unscheduled visits will be considered for deriving analysis visit. Assessments 'prior to Day X' will be identified using study day of assessments prior to Day X. The outcome of PCR-corrected ACPR and uncorrected ACPR at a given day is categorized as responder or non-responder to distinguish from failure used in early treatment failure, late clinical failure or late parasitological failure. With this notation, ACPR rate is the proportion of responders.

Recurrence of parasitaemia after 7 days is considered as non-responder for uncorrected ACPR. We reclassify such patient as responder for PCR-corrected ACPR at the visit if recurrence of parasitaemia after 7 days is due to new infection and a patient did not take rescue medication. A new infection at a visit causes PCR-corrected ACPR status unknown at later visit(s). Whether the recurrence of parasitaemia after 7 days is due to recrudescence or new infection is determined and provided by the central laboratory. Negative PCR will be handled similarly to new infection and categorize the patient as PCR corrected responder.

The above definitions of ACPRs are purely based on the malaria blood film and PCR results without consideration for taking concomitant anti-malaria drugs. In statistical analyses, some responses may be overridden for patients who take concomitant anti-malaria drugs (see [Sections 2.5 and 2.7](#)).

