2.5.3 Handling of missing values/censoring/discontinuations for primary endpoint analysis

Parasite assessments obtained within the visit window for Day 29 (Day 25 to Day 33) will be considered as the assessment for Day 29.

No missing data are expected for the primary efficacy analysis based on PPS since patients who are not evaluable for the primary efficacy variable are excluded from PPS. See [Section 2.5.4](#) for missing data handling for the supportive analysis using FAS.

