5.1.4 Visit windows

When visit windows are used, all visits will be re-aligned, i.e., they will be mapped into one of the visit windows. E.g., if the Day 4 visit of a patient is delayed and occurs on Day 7, say, it will be re-aligned to visit window Day 8. In the case of major deviations from the visit schedule, or due to unscheduled visits, several assessments of a patient may fall in a particular visit window (either scheduled or unscheduled). Statistical approaches to handle multiple assessments in a given visit window are specified below.

- Of note, patients are allowed to have gaps in visits. All data collected will be displayed in listings.
- Lower limit and upper limit of the Day 29 visit is set to be Day 27 and Day 33 respectively, with narrow window since this is the primary analysis timepoint.
- The following rules are used to determine the window for other visits post baseline:
 - “Lower limit” = “upper limit of prior applicable visit” + 1.
 - “Upper limit” = “target day of current visit” + integer part of (“target day of next applicable visit” – “target day of current visit”)/2 with the exception of Day 29
 - No upper limit for Day 43 visit
 - Upper limit of Day 15 is one day before the lower limit of Day 29

For assessments that are scheduled to be performed only once on a day, [Table 5-5](#) describes the analysis windows mapping to visits (not just scheduled visits) based on study days alone. For the assessments that may be performed on multiple timepoints on a day, [Table 5-6](#) describes the analysis windows mapping to visits based on study day and time. Repeat and/or unscheduled visits (which will be numbered in the database according to new NCDS standards) will be mapped for analysis purposes in the same way. If there are multiple measurements within an analysis window, the conventions defined in [Table 5-7](#) will be used to determine the appropriate measurement to be selected for analysis.

The mapped visits will be used in the by visit analyses. However, the listings will show all collected data regardless of used in the by visit analyses.

Table 5-5 Analysis visit windows based on study days alone

Analysis Visit	Target Day	Analysis window for assessment group		
		Vital signs/ Chemistry/ Hematology/ Urinalysis	Thyroid function	
Baseline	1	Up to Day 1	Up to Day 1	
Day 2	2	Day 2	NA	
Day 3	3	Day 3	NA	
Day 4	4	Day 4	NA	
Day 5	5	Day 5 - 6	NA	
Day 8	8	Day 7 - 11	NA	
Day 15	15	Day 12 - 26	Day 2 - 29	
Day 29	29	Day 27 - 33	NA	

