13. Other Plasmodium species before Day (D) (in the absence of P. falciparum).	If taking non-study drug prior to D29, excluded from PPS; otherwise, responder/ KM-censoring	If taking non-study drug prior to D29, excluded from PPS; otherwise, Responder/ KM-censoring	Responder/ KM-censoring	Responder/ KM-censoring
14. Other Plasmodium species before or on Day (D) (in the presence of P. falciparum), PCR-analysis result missing or indeterminate.	Handled as the Criteria 10, 12, and 13	Handled as Criteria 10, 12, and 13	Handled as Criteria 10, 12, and 13	Handled as Criteria 10, 12, and 13
15. Prematurely study discontinued from the study without parasite re-emergence before Day (D) and received SoC.	If discontinued before D29, excluded from PPS; if D=43,	If discontinued before D29, excluded from PPS; if D=43, non-	Non-responder/KM-censoring	Non-responder/KM-censoring

	Non-responder/KM-censoring	responder/KM-censoring		
16. Missing assessment on Day (D), no more assessments thereafter.	If D ≤ 29, excluded from PPS; Otherwise: non-responder/KM-censoring	If D ≤ 29, excluded from PPS; Otherwise: non-responder/KM-censoring)	Non-responder/KM-censoring	Non-responder / KM-censoring
17. Prematurely discontinued from the study before Day (D) and no record of SoC.	Same as Criterion 16	Same as Criterion 16	Same as Criterion 16	Same as Criterion 16

Note: '/' indicates separate analysis, e.g., 'non-response/KM-censoring' indicates one analysis considering outcome as non-responder and another analysis using KM method considering outcome as censored

NA: Not applicable; SoC: Standard of care

If a scenario meets multiple criteria, the worst case (non-responder) is used.

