5.8 Rule of exclusion criteria of analysis sets

Table 5-14 Protocol deviations and non-PD criteria leading to exclusion from analysis sets

Analysis Set	PD (Description and ID) that causes Patients to be excluded	Non-PD criteria that cause Patients to be excluded
Randomized	
 Informed Consent for study participation or parental consent not obtained and patient entered trial (INCL05) 	
 Not randomized Misrandomized if identified from IRT
FAS	NA	
 Not in Randomized set Baseline parasitaemia count is 0 or missing No study drug taken
PPS	
 Parasite specie is other than Plasmodium falciparum OR mixed infection (INCL03) Baseline plasmodium falciparum parasite count <1000/uL or ≥150000/uL (INCL04) at the time of prescreening for the Run-in; plasmodium falciparum parasite count < 1,500 or ≥ 150,000 /uL parasites/μL at the time of pre-screening for Cohorts 1 and 2 No fever within the past 24 hours at baseline (INCL06) Prohibited non-antimalarial medications that may have effect on efficacy if received before the Day 29 visit without being falciparum treatment failures (COMD001A) Only for Run-in Cohort, do not fully comply with the food guidelines according to randomization (with OTH04 either day) 	
 Not in FAS; <80% of randomized study medication taken Received non-study concomitant antimalarial drugs during the treatment period Received non-study concomitant antimalarial drugs after the treatment period between Day 4 and Day 29 without experiencing treatment failure Not classified as non-responder before Day 8, no positive blood smear parasite on Day 8 onwards, and blood smear parasite result is missing at Day 29 and later (early discontinued) Not classified as non-responder before Day 8, have at least one positive blood smear parasite result between Day 8 and Day 29 which cannot be determined as recrudescent or new infection based on PCR genotyping and have parasites cleared prior to the positive blood smear parasite; Not classified as non-responder before Day 8, have a new infection prior to study Day 27 and have

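### SAP 2.1.1.2 defines 'Day 29' by analysis window but 'prior to Day 29' by study day, so a new infection on study Day 27 or 28 has conflicting primary outcomes

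*SAP*

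**What the plan says.** The Note in SAP 2.1.1.2 sets two clocks. For the visit itself, "the 'Day X' is referred to as the Day X analysis visit", and "Analysis visit X will be derived using the day actual visit as defined in Tables 5-5 and 5-6". SAP 5.1.4 gives the window: "Lower limit and upper limit of the Day 29 visit is set to be Day 27 and Day 33 respectively". For what came earlier, assessments "will be identified using study day of assessments prior to Day X".

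The rules that use these terms point in different directions for PCR-corrected ACPR at Day 29:

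- **Responder or retained.** One bullet of 2.1.1.2 makes a new infection at Day X a responder, "using PCR genotyping or later if Day X is missing". Criterion (e) of the per-protocol set (SAP 2.2) treats a new infection at the Day 29 visit as a defined status. Table 5-13 row 8 gives responder. Table 5-14 removes from the per-protocol set only cleared children who "have a new infection prior to study Day 27".
- **Undetermined or excluded.** Another bullet of 2.1.1.2 makes the response missing or undetermined if a new infection came before Day X. SAP 2.7.2.1 excludes from the per-protocol set new infections from Day 8 up to Day 29, and Table 5-13 row 9 does the same for D ≤ 29.

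The primary hypothesis is tested on the per-protocol set (SAP 2.5.2).

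**The concern.** Study Days 27 and 28 lie inside the Day 29 analysis visit but before study Day 29. Read literally, a child whose new infection is found on one of those days meets the responder bullet and the undetermined bullet at once. Two programmers could both follow the SAP and build different primary datasets: one with the child in the per-protocol set as a responder, one with the child left out. A third would keep the child, as Table 5-14 directs, with an undetermined response, although SAP 2.5.3 expects no missing primary outcomes in that set. The treatment is open to patients and investigators, so a choice between these readings is better made before the data are locked than after.

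**Working it through.** **1. The plan's own figure.** Inputs from SAP 3.1.1: 95% response in both arms, margin 10 points, one-sided alpha 2.5%, 92 evaluable per arm, stated power at least 87%.

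Power = Φ(0.10 / √(2 × 0.95 × 0.05 / 92) − 1.96) = 87.5%. Evaluable per arm = 220 × 0.84 / 2 = 92.4. Both agree with the plan.

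**2. Which days conflict.** Each study day of a PCR-confirmed new infection (initial parasites cleared) set against the rules:

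| Study day | Visit by Table 5-6 | In the 2.5.3 window (25–33) | Table 5-14 | Before study Day 29 |
|---|---|---|---|---|
| 24 | Day 15 | no | removed | yes |
| 25–26 | Day 15 | yes | removed | yes |
| 27–28 | Day 29 | yes | kept | yes |
| 29–33 | Day 29 | yes | kept | no |

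Only Days 27 and 28 are in the Table 5-6 Day 29 window, kept by Table 5-14 and literally before study Day 29. The row for Days 25–26 shows a separate discrepancy: SAP 2.5.3 says "Parasite assessments obtained within the visit window for Day 29 (Day 25 to Day 33) will be considered as the assessment for Day 29", whereas 5.1.4 starts the window at Day 27.

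**3. Two assessments in one window.** Unscheduled visits count when the analysis visit is derived (2.1.1.2). Suppose an unscheduled smear on Day 27 or 28 shows a new infection and the scheduled smear follows on Day 29. Table 5-7 takes the measurement closest to the target day, so the Day 29 smear represents the visit. The infection is then not the selected result for Day 29, and by study day it came earlier. The sentence in 2.1.1.2 that reclassifies a new infection as a responder also requires that no rescue medication was taken, so rescue medication started after the Day 27 or 28 finding would remove that route too.

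**4. Size in the per-protocol set.** The choice there is responder versus excluded or undetermined. The documents give no count of affected children, so the illustration takes k = 1 to 4 in the test arm, from an assumed 87/92 in each arm (0.95 × 92 = 87.4). The interval is the Wilson uncorrected difference of SAP 5.7.1: lower limit = d − √{(p₁ − l₁)² + (u₂ − p₂)²}, with Wilson limits l and u for each arm.

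| k | Test arm if excluded | Lower limit |
|---|---|---|
| 0 (or all scored as responders) | 87/92 = 94.6% | −7.3% |
| 1 | 86/91 = 94.5% | −7.5% |
| 2 | 85/90 = 94.4% | −7.6% |
| 3 | 84/89 = 94.4% | −7.7% |
| 4 | 83/88 = 94.3% | −7.8% |

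Simple Wald limits run from −6.55% (k = 0) to −6.94% (k = 4). If k children are lost from both arms, planned power falls from 87.5% to 87.2% (k = 1) and 86.1% (k = 4). The planned pooled analysis is a Mantel-Haenszel difference stratified by cohort, so these single-stratum figures show scale only.

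**The case against.** The best answer is that the SAP, read as a whole, leads to responder. The undetermined bullet carries its own gloss, repeated after the Note, that a new infection makes status unknown at later visits, not at the visit where it is found. Criterion (e) and Table 5-13 row 8 agree. Since Day X means the analysis visit, 'prior to Day X' can be taken as before that visit, and Table 5-14 uses exactly that boundary. For the full analysis set, SAP 2.5.4 and 2.7.2.1 already specify one analysis with earlier new infections as responders and one as non-responders.

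Much of this stands, and it rules out two stronger readings. A reader might infer that these children sit in the per-protocol set with no defined outcome. The documents do not support that: they give competing outcomes, and several passages supply responder. A reader might also infer from the note to Table 5-13, "If a scenario meets multiple criteria, the worst case (non-responder) is used", that the children become non-responders in the primary analysis. On the assumed counts above, two such test-arm cases would take the lower limit to −10.1%. But for D ≤ 29 the per-protocol entry in row 9 is exclusion, so neither row scores them as per-protocol non-responders.

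The objection does not remove the contradiction. The Note is the express rule for 'prior to Day X', and it says study day. SAP 2.7.2.1 and Table 5-13 row 9 do not carry the Day 27 boundary of Table 5-14. The gloss also leaves open the case of two assessments in one window.

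**Conclusion.** The primary-endpoint rule contradicts itself for new infections on study Days 27 and 28 and should be corrected. The effect on the primary result is likely to be slight: a few tenths of a point on the lower limit for one to four one-sided cases, under the assumed 87/92 per arm. The number of such children cannot be taken from the documents. It is probably small, because it needs an early or unscheduled visit on one of two days.

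The same overlap arises at Day 15 (study Days 12–14) and Day 43 (study Days 34–42) but matters less. Table 5-14 already removes the Day 15 cases from the per-protocol set, both scorings are specified at Day 43, and SAP 2.7.2 treats these endpoints as supportive.

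**What to change.** Define 'prior to Day X' as before the lower limit of the Day X analysis window, which for Day 29 means before study Day 27, as Table 5-14 already has it. Apply this in the Note of 2.1.1.2, in 2.5.4, in 2.7.2.1 and in Table 5-13 rows 8 and 9. Add a sentence that a new infection found anywhere in the window determines status at that visit, even if a later smear in the window is closer to the target day, and say how the no-rescue condition in 2.1.1.2 applies to such a child. Align the window in 2.5.3 with 5.1.4, since the new definition depends on a single lower limit.

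The cost is a few SAP sentences and two table rows before database lock, with no new data and no change to the trial's conduct.

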### 6.2.3 Rescue medication

The following circumstances warrant discontinuation of study treatment and the implementation of rescue medication:

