#### 12.4.4 Sensitivity analyses

- For patients who have a reinfection after 7 days but prior to Day 29 visit, such as at Day 15, the statistical method specified in [Section 12.4.2](#) will be performed by assigning treatment failure to these patients.
- The primary efficacy variable will be performed based on the FAS using the statistical method specified in [Section 12.4.2](#). Missing primary efficacy variable will be handled as follows:
  - Patients who received rescue medication for the treatment of *P. falciparum* malaria (except for the treatment of a new infection) will be considered treatment failures (from the day of rescue use onwards).
  - Patients who received other concomitant medication having an effect on malaria for reasons other than rescue therapy e.g. for the treatment of *P. vivax* [REDACTED]

(e.g., primaquine, certain antibiotics (sulfonamides, tetracycline, etc.)) will be considered in the analysis as if they had not taken the drug.

- Patients will be counted as failure if (a) they did not have a parasite count assessment at Day 29 unless these patients could be classified as cured based on absence of parasitemia at later time, or (b) they did not have valid PCR evaluations at baseline and Day 29 if parasitemia was present at Day 29.
- In addition, for the FAS, the proportion of patients with PCR-corrected ACPR at Day 29 and 95% CI by treatment group and the difference will be also estimated using the Kaplan-Meier method (Stepniewska and White 2006 and WHO 2015) which uses treatment failure as the event and treats missing data as censored instead of treatment failure. The PCR-corrected ACPR rate at Day 29 is estimated by the survival function at Day 29. Patients who had a new infection (i.e., reinfection) with *P. falciparum* or other species without *P. falciparum* recrudescence on or after Day 8 will be censored at the time of the first PCR that indicate the infection; patients who took antimalarial medications for reinfection or reasons other than rescue medication given for signs and symptoms of infection with *P. falciparum* or unsatisfactory therapeutic effect will be censored at the first time of such antimalarial medications; other patients without treatment failure will be censored at the time of the last parasitemia assessment. A two-sided 95% CI for the difference in proportion between the 2 treatment groups will be calculated based on the variance of individual proportion using the Greenwood formula.

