2.5.4 Sensitivity analyses

- The primary efficacy analysis will be repeated on the FAS using the statistical methods specified in [Section 2.5.2](#). Primary efficacy variable will be handled additionally for those patients who are excluded from the PPS as follows:
 - Presence of parasitaemia which cannot be determined to be recrudescence or new infection due to missing PCR data will be counted as non-responders (from the day of test)
 - Missing/undetermined responses at Day 29 due to missing blood smear data at the visit will be counted as non-responders unless there is a later blood smear test indicating no parasitemia.
 - Patients with new infection before Day 29 will be considered 1) not achieving PCR-corrected ACPR at Day 29 in one analysis and 2) and achieving PCR-corrected ACPR at Day 29 in another analysis
 - Patients who received non-study related anti-malarial medication without having reappearance of the parasites will be considered in the analysis as if they had not taken these drugs. This is because such cases will be very unlikely as administration of such medicines are expected only in case of the reappearance of the parasites. Note- Patients who take non-study anti-malarial medication due to repeated vomiting of study medication should be considered as treatment failure.

Note: These patients did not experience any treatment failure (ETF, LCF, or LPF). In case that non-PPS patients who experienced treatment failure, they will be included as non-responders if they received rescue medication for the treatment of *P. falciparum* malaria due to recrudescence or as responder for PCR corrected ACPR if they received rescue medication to treat a new infection on Day 29 visit.

- Patients who received non anti-malaria medication with potential anti-malarial activity without having reappearance of the parasites will be considered in the analysis as if they had not taken these drugs. This is because such medications will have minimal effect on efficacy.

- Although the objective of Run-in cohort is to investigate the food effect on bioavailability of KAF156 and lumefantrine, analyses related to primary and other secondary variables will be performed in Run-in cohort by treatment group, unless otherwise specified.

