5.7.4 Summary of treatment outcome assignment

The below table provides treatment outcome assignments for both uncorrected and PCR-corrected ACPR at a given Day, say D where D can be 15, 29, or 43, for various specific scenarios.

Table 5-13 Derivation Criteria of uncorrected ACPR and PCR- corrected ACPR

Criteria	PP Analysis Set (PPS)		ITT Analysis Set	
	Treatment Outcome uncorrected ACPR	Treatment Outcome PCR-adjusted ACPR	Treatment Outcome uncorrected ACPR	Treatment Outcome PCR-adjusted ACPR
1. Completed up to Day (D) without re-emergence (new infection/ recrudescence) of parasites after initial clearance	Responder	Responder	Responder	Responder
2. Missing assessment on Day (D), but parasite free (No P. falciparum asexual parasites) after Day (D).	Responder	Responder	Responder	Responder
3. Missing assessment on Day (D), new infection (confirmed by PCR result) at first assessment after Day (D).	Non-responder	Responder	Non-responder	Responder
4. Early treatment failure from Day 2 to Day 4.	Non-responder	Non-responder	Non-responder	Non-responder
5. Late clinical failure from Day 5 to Day 7.	Non-responder	Non-responder	Non-responder	Non-responder
6. Receive non-study anti-malarial medication during the treatment period	Excluded from PPS	Excluded from PPS	Non-responder	Non-responder
7. Recrudescence before or on Day (D) (thus on or after Day 8 to [D])	Non-responder	Non-responder	Non-responder	Non-responder
8. New infection/PCR negative on Day (D).	Non-responder	Responder	Non-responder	Responder
9. New infection/PCR negative before Day (D) (thus on or after Day 8 to before (D))	If D <=29, excluded from PPS; If D=43, Non-responder	If D <= 29, excluded from PPS; if D=43, non-responder/	Non-responder	Non-responder/responder/KM-censoring

		responder/KM-censoring;		
10. Re-emergence before or on Day (D) but PCR result is indeterminate or missing.	Non-responder	Excluded from PPS if D ≤ 29 or non-responder/KM-censoring if D=43	Non-responder	Non-responder/KM-censoring
11. Missing assessment on Day (D), recrudescence (confirmed by PCR result) at first assessment after Day (D).	If D=29, excluded from PPS; if D=15, non-responder/KM-responder; NA for D=43	If D=29, excluded from PPS; if D=15, non-responder/ KM-responder; NA for D=43	Non-responder/ KM-responder	Non-responder/ KM-responder
12. Other Plasmodium species on Day (D) (in the absence of P. falciparum).	Responder	Responder	Responder	Responder

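### One clause in SAP 2.1.1.2 makes PCR-corrected response after a new infection depend on no rescue being taken, in conflict with the primary endpoint rules elsewhere

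*SAP*

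**What the plan says.** SAP 2.1.1.2 defines PCR-corrected ACPR in a bullet list. One bullet makes a child who is not already a non-responder a responder at Day X when "the patient has a malaria blood film showing new infection" at that visit by genotyping, or later if Day X is missing. It says nothing about rescue.

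A paragraph after the list restates the rule. It reclassifies a recurrence after 7 days as a PCR-corrected responder "if recurrence of parasitaemia after 7 days is due to new infection and a patient did not take rescue medication". It does not say whether this means rescue before, at or after the visit. The next paragraph says the definitions are "purely based on the malaria blood film and PCR results without consideration for taking concomitant anti-malaria drugs" and that Sections 2.5 and 2.7 may override some responses.

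Protocol 6.2.3 introduces early treatment failure (ETF), late clinical failure (LCF) and late parasitological failure (LPF) with "The following circumstances warrant discontinuation of study treatment and the implementation of rescue medication". LCF and LPF together cover any parasitaemia from Day 8 to Day 43, with no genotyping distinction. The section also leaves the start of rescue to the investigator. Protocol 4.5 foresees standard-of-care treatment for any new infection.

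**The concern.** A child treated as the protocol foresees for a new infection at the Day 29 visit fails the clause as worded. If the clause were programmed, PCR correction would be lost for that child. The primary comparison would then partly reflect protection against reinfection after treatment, which may differ between arms, and not only cure of the treated infection.

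The visit matters because the assessment schedules contain no film between Day 15 and Day 29 other than unscheduled ones. Symptomless new infections from that interval would mostly be found at Day 29. SAP Section 4 declares no change from the protocol's analyses, yet the clause read literally departs from protocol 12.4.1.

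**Working it through.** **1. One child through the passages.** Parasites clear before Day 8. The Day 29 film is positive. The genotyping sample is taken before treatment (protocol 6.2.3), an antimalarial is given, and the central laboratory later reports a new infection. SAP 2.4.2 calls that drug rescue, because it follows LCF or LPF.

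| Place | PCR-corrected result at Day 29 | Applies to |
|---|---|---|
| SAP 2.1.1.2, explanatory paragraph, read literally | Non-responder | Definition |
| SAP 2.1.1.2, bullet | Responder | Definition |
| SAP Table 5-13, row 8 | Responder | PPS and ITT |
| Protocol 12.4.1 | Not a failure | Primary endpoint |
| Protocol 12.4.4: "Patients who received rescue medication for the treatment of *P. falciparum* malaria (except for the treatment of a new infection) will be considered treatment failures" | Not a failure through rescue | FAS |
| SAP 2.5.4: "as responder for PCR corrected ACPR if they received rescue medication to treat a new infection on Day 29 visit" | Responder | Non-PPS patients in the FAS |

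**2. Does the child reach the primary analysis?** Testing is on the PPS (SAP 2.5.2). SAP 2.2 criterion (e) keeps new infections at the Day 29 visit or later, and Table 5-14 removes those before study Day 27. Antimalarial use after a treatment failure is not a reason for exclusion. The exposed group is therefore new infections in the Day 27 to 33 window of SAP 5.1.4, or later if Day 29 is missing. (SAP 2.5.3 still gives Day 25 to 33 for that window.)

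**3. The plan's own power.** Inputs: 95% response in both arms, margin 10 points, one-sided 2.5%, 92 per arm.
- SE = sqrt(2 × 0.95 × 0.05 / 92) = 0.0321
- Power = Φ(0.10 / 0.0321 − 1.960) = Φ(1.152) = 87.5%, against the stated figure of at least 87%
- 92 / 0.84 = 109.5, so 110 per arm and 220 in all, as stated

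**4. Effect on the confidence limit (counts assumed).** I split 92 per arm into 58 in Cohort 1 and 34 in Cohort 2 (140 × 0.84 / 2 = 58.8; 80 × 0.84 / 2 = 33.6). Each arm has 5 recrudescences, 3 and 2 by cohort. The method is the Mantel-Haenszel risk difference stratified by cohort, with the Sato variance. For a cohort with n per arm and x1 (KAF156/LUM-SDF) and x2 (Coartem) responders:
- d = Σ[(x1 − x2)/2] / Σ(n/2)
- P = Σ(x2 − x1)/4
- Q = Σ[x1(n − x2) + x2(n − x1)]/(4n)
- Var = (dP + Q) / [Σ(n/2)]², with Σ(n/2) = 29 + 17 = 46

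*New infections scored as responders:* 55 v 55 of 58 and 32 v 32 of 34.
- d = 0; Q = 1.422 + 0.941 = 2.364
- SE = sqrt(2.364)/46 = 0.0334; lower limit −6.6%

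*Four KAF156/LUM-SDF and two Coartem new infections, all rescued, scored by the clause:* 53 v 54 of 58 and 30 v 31 of 34.
- d = −1/46 = −2.2%; P = 0.5; Q = 2.078 + 1.574 = 3.651
- SE = sqrt(−0.0217 × 0.5 + 3.651)/46 = 0.0415
- Lower limit = −2.17% − 1.96 × 4.15% = −10.3%

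Other assumed counts, scored by the clause:
- 3 v 3: lower limit −8.1%
- 2 v 0: −9.3%
- 3 v 0: −10.7%
- 2 v 4: difference +2.2%, lower limit 2.17% − 8.13% = −6.0%

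**5. Effect on power (rates assumed).** Let q be the share of the PPS with a rescued new infection at that visit. Scored by the clause, response falls to 95% − q. With equal q in both arms, power is 81.5% at 1%, 75.7% at 2%, 70.5% at 3% and 61.8% at 5%. With 5% on KAF156/LUM-SDF and 2% on Coartem it is 39.9%. With the reverse it is 88.6%.

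**The case against.** The best defence is that the operative rules already agree. The bullet, Table 5-13 row 8 and protocol 12.4.1 all make this child a responder. The SAP's change log says that table was added at the latest revision to describe the derivation. The note under it, which takes the worst case when several rows apply, does not displace row 8, because no row penalises rescue after a new infection. The clause can also be read as no rescue before that visit, which would remove the conflict.

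Most of this stands. The clause is one sentence outweighed by the rest, so a reader who infers that the SAP turns every rescued reinfection into a non-response takes one reading as settled. Nor do the documents support inferring that rescue is compulsory at every recurrence: protocol 6.2.3 says failures warrant it but leaves the start to the investigator. Protocol 12.4.4 and the SAP 2.5.4 note govern FAS handling, so they support the other side without settling the PPS case.

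What does not fall away is the ambiguity. The clause sets no timing, and the section contradicts itself in its next paragraph. The override it points to in Section 2.5 covers only children outside the PPS.

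**Conclusion.** The inconsistency is real and lies in the classification of the primary endpoint in the primary analysis set. It is limited to rescued new infections at the Day 29 visit, or later if that film is missing. Earlier new infections are excluded from the PPS and are analysed both ways in the FAS.

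The documents give no reinfection rate, so every count and rate above is an assumption. Under those counts, an excess of 2 or 3 rescued new infections on KAF156/LUM-SDF takes the lower limit past −10% (4 v 2 or 3 v 0). The 3 v 3 example still meets the margin, and an excess on Coartem favours KAF156/LUM-SDF. The choice of passage could therefore change the non-inferiority conclusion. The documents do not show that it will, or in which direction. Two programmers working from this SAP could derive different primary results, which is reason enough to settle the wording.

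**What to change.** In SAP 2.1.1.2, delete the words making the absence of rescue medication a condition of reclassification. Add that rescue started at or after the film showing the PCR-confirmed new infection does not change PCR-corrected status at that visit. This agrees with protocol 12.4.1, the bullet in the same section and Table 5-13 row 8. Then check that the derivation program follows it.

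Limiting the clause to antimalarials taken before the recurrence would not work. Under SAP 2.4.2 such drugs are not rescue. Their use before Day 29 already excludes the child from the PPS (SAP 2.2 and Table 5-14), and SAP 2.5.4 generally disregards it in the FAS.

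The cost is one edit and a program check. No new data are needed, and the change concerns outcome classification only, not when rescue is given.
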